5.2 Selection of Study Population

5.2.1 Inclusion Criteria

Subjects must have generalized pustular psoriasis or erythrodermic psoriasis.

General Inclusion Criteria

1. Male or female subjects, age ≥ 20 years at screening.
2. If female, subject must be either postmenopausal defined as:
 - Age ≥ 55 years with no menses for 12 or more months without an alternative medical cause.
 - Age < 55 years with no menses for 12 or more months without an alternative medical cause AND an FSH level > 40 IU/L OR
 - Permanently surgically sterile (bilateral oophorectomy, bilateral salpingectomy or hysterectomy)
OR
 - Women of Childbearing Potential (WOCBP) should be practicing at least one protocol specified method of birth control (Section 5.2.4) starting on Study Day 1 (or earlier) through at least 16 weeks after the last dose of study drug.

3. Females of childbearing potential must have a negative serum pregnancy test result at screening, and a negative urine pregnancy test at Study Day 1.
Females of non-child bearing potential (either postmenopausal or permanently surgically sterile as defined above) at screening do not require pregnancy testing at study Day 1.
4. Signed and dated written informed consent prior to admission to the study in accordance with Good Clinical Practice and local legislation.

Disease Specific Inclusion Criteria

For Generalized Pustular Psoriasis

5. Have a diagnosis of generalized pustular psoriasis for at least 60 days prior to informed consent based on the diagnostic criteria of the Japanese Dermatological Association (JDA). Subjects not fulfilling one of the diagnostic criteria i.e., "accompanying systemic symptoms including fever or malaise" at the time of screening can be entered.
6. Subjects with an erythema area with pustules accounting for $\geq 10\%$ of the body surface area (BSA), and with a severity assessment criteria score (JDA total score) specified by the JDA of less than 14 ([Appendix D](#)).
7. Must be candidates for systemic therapy or phototherapy for generalized pustular psoriasis, as assessed by the investigator.

For Erythrodermic Psoriasis

8. Have a diagnosis of erythrodermic psoriasis prior to informed consent.
9. Subjects with an inflammatory erythema area accounting for $\geq 80\%$ of the BSA at screening and at the time of the first administration of the study drug.
10. Must be candidates for systemic therapy or phototherapy for erythrodermic psoriasis, as assessed by the investigator.

5.2.2 Exclusion Criteria

A subject will not be eligible for study participation if he/she meets any of the following criteria:

General Exclusion Criteria

1. Previous exposure to risankizumab.
2. Currently enrolled in another investigational study or less than 30 days (from screening) since completing another investigational study (participation in observational studies is permitted),
3. Use of any restricted medication as specified in [Table 1](#) or any drug considered likely to interfere with the safe conduct of the study.
4. Major surgery performed within 12 weeks prior to assignment or planned within 12 months after baseline (e.g., hip replacement, aneurysm removal, stomach ligation).
5. Known chronic or relevant acute infections including HIV, viral hepatitis and/or tuberculosis as defined by either a positive QuantiFERON® TB test or a positive PPD (purified protein derivative) skin test. Subjects with a positive QuantiFERON® TB/PPD test result may participate in the study if further work up (according to local practice/guidelines) establishes conclusively that the subject has no evidence of active tuberculosis.
6. Any documented active or suspected malignancy or history of malignancy within 5 years prior to screening, except appropriately treated basal or squamous cell carcinoma of the skin or in situ carcinoma of uterine cervix.
7. Evidence of a current or previous disease, medical condition (including chronic alcohol or drug abuse) other than psoriasis, surgical procedure (i.e., organ transplant), medical examination finding (including vital signs and ECG), or laboratory value at the Screening Visit outside the reference range that, in the opinion of the investigator, is clinically significant and would make the study

participant unreliable to adhere to the protocol or to complete the trial, compromise the safety of the subject, or compromise the quality of the data.

8. History of allergy/hypersensitivity to a systemically administered biologic agent or its excipients.
9. Female subject who is pregnant, breastfeeding or is considering becoming pregnant during the study or for approximately 16 weeks after the last dose of study drug.
10. Previous enrollment in this trial.

Disease Specific Exclusion Criteria

For Generalized Pustular Psoriasis

11. Subjects with active ongoing inflammatory diseases other than generalized pustular psoriasis that might confound trial evaluations according to investigator's judgment.

For Erythrodermic Psoriasis

12. Subjects with active ongoing inflammatory diseases other than erythrodermic psoriasis that might confound trial evaluations according to investigator's judgment.
13. Subject diagnosed with medication-induced or medication-exacerbated EP.

5.2.3 Prior and Concomitant Therapy

Any biologic or systemic medication or vaccine for psoriasis (including over-the-counter or prescription medicines, vitamins and/or herbal supplements) that the subject has or is receiving at the time of enrollment, or receives during the study, must be recorded along with the reason for use, date(s) of administration including start and end dates, and dosage information including dose, route and frequency on the appropriate eCRF.

Complete systemic psoriasis medication history, whether biologic or not, and including phototherapy will be captured as well as topical psoriasis medicine use should be captured for the past 5 years.

Stable doses of concomitant therapies for chronic conditions, for which neither the condition nor the treatment are judged to exclude the subject from participation are permissible. All concomitant medications should be carefully evaluated by the investigator and the AbbVie TA MD should be contacted if there are any questions regarding concomitant or prior therapy(ies).

5.2.3.1 Prohibited Therapy

Uses of the following therapies are prohibited from administration in the time periods specified.

Table 1. Restricted Medications

Medication or Class of Medications	Restriction Duration (Through Week 188 Follow-Up Visit)
secukinumab (Cosentyx®), biologics targeting IL-12 except ustekinumab, IL-17 (except ixekizumab and brodalumab), and/or IL-23 directly	26 weeks prior to randomization
ustekinumab (Stelara®), Tumor Necrosis Factor (TNF)- α inhibitors except infliximab, adalimumab and etanercept	12 weeks prior to randomization
granulocyte and monocyte adsorptive apheresis (GMA)	12 weeks prior to randomization
brodalumab, ixekizumab	4 months prior to randomization
infliximab (Remicade®)	8 weeks prior to randomization
adalimumab (Humira®)	2 weeks prior to randomization
etanercept (Enbrel®) live virus vaccinations	6 weeks prior to randomization
Tofacitinib, apremilast	30 days prior to randomization
any investigational device or product (excludes psoriasis products)	30 days prior to randomization
investigational drug for psoriasis (biologics and non-biologics)	12 weeks prior to randomization, or five half-life if longer
other systemic immunomodulating treatments (e.g., methotrexate, cyclosporine A, corticosteroids, ^a cyclophosphamide)	These therapies have to be unchanged for at least 4 weeks prior to randomization, and any change in the dose should be avoided.
other systemic psoriasis treatments (e.g., retinoids, fumarates, any other drug known to possibly benefit psoriasis)	After Week 16, only dose decreasing will be permitted. Cyclosporine A and systemic corticosteroid will be tapered off after confirmation of a clinical improvement in the opinion of the investigator.
phototherapy (e.g., PUVA)	4 weeks prior to assignment
phototherapy (e.g., UVA, UVB)	2 weeks prior to assignment
topical treatment for psoriasis or any other skin condition (e.g., corticosteroids, ^b vitamin D analogues, vitamin A analogues, retinoids, salicylvaseline, salicylic acid, lactic acid, tacrolimus, tar, urea, α -hydroxy acid [fruit acids])	2 weeks prior to randomization

- a. No restriction on corticosteroids with only a topical effect (e.g., inhalative corticosteroids to treat asthma or corticosteroid drops used in the eye or ear).
- b. Exception: Topical steroids of mild potency such as locoid or weak potency such as prednisolone for use on the face, axilla, and/or genitalia with a restriction of use within 24 hours prior to trial visit in which PASI is assessed.

5.2.3.2 Rescue Therapy

There are no special emergency procedures to be followed.

In the event that a subject experiences an intolerable worsening of GPP or EP, as deemed by the investigator, during the course of the trial the subject will be discontinued from the trial to receive rescue treatment.

In case of adverse events in need of treatment, symptomatic therapy according to investigator judgment will be permitted. All concomitant and/or rescue therapies will be recorded on the appropriate pages of the eCRF.

5.2.4 Contraception Recommendations and Pregnancy Testing

Women of child bearing potential should practice at least one of the following methods of birth control, on Study Day 1 (or earlier) through at least 16 weeks after the last dose of study drug.

Combined (estrogen and progestogen containing) hormonal contraception (oral) associated with the inhibition of ovulation, initiated at least 1 month prior to Study Day 1.

Progestogen-only hormonal contraception (oral) associated with inhibition of ovulation, initiated at least 1 month prior to Study Day 1.

Bilateral tubal occlusion/ligation.

Vasectomized partner(s), provided the vasectomized partner has received medical assessment of the surgical success and is the sole sexual partner of the WOCBP trial participant.

Intrauterine device (IUD).

Intrauterine hormone-releasing system (IUS).

True abstinence: Refraining from heterosexual intercourse when this is in line with the preferred and usual lifestyle of the subject (periodic abstinence [e.g., calendar, ovulation, symptothermal, post-ovulation methods] and withdrawal are not acceptable).

5.3 Efficacy, Pharmacokinetic and Safety Assessments/Variables

5.3.1 Efficacy and Safety Measurements Assessed

Study procedures described are listed in the following section of this protocol and are summarized in tabular format in [Appendix C](#).

5.3.1.1 Study Procedures

Informed Consent

The subject will sign and date a study specific, Independent Ethics Committee (IEC)/Independent Review Board (IRB) approved, informed consent form before any study specific procedures are performed in order to participate in this study. Details regarding how informed consent will be obtained and documented are provided in [Section 9.3](#).

Inclusion/Exclusion Criteria

Subjects will be evaluated to ensure they meet all inclusion criteria and have none of the exclusion criteria at both the Screening and the Week 0 visit.

Demographics

The subject's demographic data, including date of birth, gender, race, ethnicity, and disease status will be collected at the Screening Visit.

Physical Examination

Complete and targeted physical examinations will be performed at visits as described in [Appendix C](#). Complete physical examination will include general appearance as well as

evaluation of all relevant organ systems. Targeted physical examination will include vital signs assessment and evaluation of organ systems associated with AE(s) symptoms or laboratory abnormalities.

Physical examination findings that are related to subject's medical history will be captured on the appropriate medical history eCRF.

Vital Signs

Vital sign assessment includes temperature, pulse rate, sitting blood pressure, and respiratory rate, after subjects have been seated comfortably for at least 5 minutes.

Measurement of vital signs should precede blood sampling and be assessed pre-dose at all dosing visits. At Visit 2 and Visit 3 additional vital signs will be taken at 5 minutes post-dose and 60 minutes post-dose.

Subjects should be closely monitored for signs and symptoms of hypersensitivity reactions for approximately 2 hours after the first dose administered and 1 hour following all other doses of study drug. Hypersensitivity reactions should be treated according to medical standards. Pre-medications for further injections might be considered and will be agreed on between investigator and AbbVie TA MD.

Body Weight and Waist Circumference

Waist circumference measurements should be made around a subject's bare midriff, after the subject exhales while standing without shoes and with both feet touching and arms hanging freely. The tape should be placed perpendicular to the long axis of the body and horizontal to the floor and applied with sufficient tension to conform to the measurement surface. Waist circumference should be determined by measuring the midpoint between the lowest rib and the iliac crest.

Body weight measurements should be done on the same scale for each subject. In order to get comparable body weight values, it should be performed in the following way:

- fasting (except for the Screening Visit)
- after the urine sampling (body weight after bladder voiding)
- shoes and coat/jackets should be taken off
- pockets should be emptied of heavy objects (i.e., keys, coins, etc.)

Electrocardiogram

The 12-lead ECGs will be performed as scheduled in [Appendix C](#).

The ECG will be recorded after the subjects have rested for at least 5 minutes in a supine position and will always precede blood sampling. Six limb leads, as specified by Einthoven (I, II and III) and Goldberger (aVR, aVL, aVF), and six pre-cordial leads (V1 – V6), according to Wilson, will be used.

The ECG may be repeated for quality reasons and the repeat used for analysis. Additional ECGs may be collected for safety reasons. Clinically relevant, abnormal findings will be reported as AEs.

Information about the details of ECG collection and the parameters assessed will be provided in the ISF.

The electronic version of the ECG is regarded as source data.

Pregnancy Testing

A serum pregnancy test will be performed for all female subjects at the Screening Visit. A urine pregnancy testing will be done on all women of child-bearing potential prior to administration of study drug at all dosing visits and at each Follow-Up Visit. Additional serum pregnancy testing will occur in case of a positive urine test result at any of the visits and must be negative to further treat the subject.

Females of non-childbearing potential (either postmenopausal or permanently surgically sterile as defined in Section [5.2.4](#)) do not require pregnancy testing after screening.

Safety Laboratory Parameters

The laboratory tests listed in [Table 2](#) will be performed by the central laboratory service provider at Visits 1, 2, 4, 6, 8, 10, 12, 16, 20, EOT and at Week 188 follow-up visit ("complete" lab). At Visits 3, 5, 7, 9, 11, 13, 14, 15, 17, 18, 19, 21, only WBC, serum CRP and serum albumin will be collected ("targeted" lab). A local laboratory may be used for selected tests in exceptional cases. Subjects should be fasting for at least 8 hours prior to the blood sample being taken at the "complete" visits, except for screening (see [Appendix C](#)).

Instructions regarding sample collection, sample handling/processing and sample shipping are provided in the Laboratory Manual in the ISF. For time points of laboratory sampling, see [Appendix C](#).

Laboratory results (i.e., all safety laboratory and clinical laboratory data relevant for current clinical practice) of the subjects will be available in real time to the respective investigator (via laboratory reports) and to the sponsor (via the central laboratory website) and selected abnormal laboratory alerts will be flagged to the site and sent to sponsor in real time.

A clinically relevant value may be either in or outside the reference range. Clinically relevant abnormal laboratory test results must be confirmed using an unscheduled visit laboratory kit and should be repeated until normalization or stabilization or until an alternative explanation has been found. Laboratory abnormalities are considered to be adverse events only if they result in discontinuation from the study, necessitate therapeutic medical intervention, and/or if the investigator considers them to be adverse events.

Table 2. Laboratory Tests

Category	Test Name
Hematology	Hematocrit (Hct) Hemoglobin (Hb) Red Blood Cell Count/Erythrocytes White Blood Cells/Leukocytes Platelet Count/Thrombocytes
Diff. Automatic	Neutrophils (relative count) Eosinophils (relative count) Basophils (relative count) Monocytes (relative count) Lymphocytes (relative count)
Diff. Manual (if Diff Automatic is abnormal)	Neutrophils, bands (Stabs) Neutrophils, polymorphonuclear (PMN) Eosinophils Basophils Monocytes Lymphocytes
Enzymes	AST(GOT) ALT(GPT) Alkaline Phosphatase (AP) Creatine Kinase (CK) CK-MB, only if CK is elevated Gamma-Glutamyl Transferase (GGT/γ-GT)
Electrolytes	Calcium Sodium Potassium Chloride Bicarbonate

Table 2. Laboratory Tests (Continued)

Category	Test Name
Substrates	Glucose BUN Creatinine eGFR (estimated by CKD-EPI formula) Bilirubin Total Bilirubin Direct (if total is elevated) Bilirubin Indirect (if total is elevated) Albumin C-Reactive Protein (CRP) (high sensitivity) Cholesterol, total Triglycerides LDL-Cholesterol HDL-Cholesterol
Urine Pregnancy test (only for female subjects of childbearing potential) ^d	Human Chorionic Gonadotropin in the urine
Serum Pregnancy test (in all female subjects at screening or if urine pregnancy test is positive)	Human Serum Chorionic Gonadotropin
Autoantibodies (only at screening)	Rheumatoid Factor
Urinalysis (dipstick)	Urine Nitrite Urine Protein Urine Glucose Urine Ketone Urobilinogen Urine Bilirubin Urine RBC/Erythrocytes Urine WBC/Leukocytes Urine pH Urine creatinine
Urine-Sediment (microscopic examination, only if urine analysis abnormal)	Urine Sediment Bacteria Urine Cast in Sediment Urine Squamous Epithelial Cells Urine Sed. Crys., Unspecified Urine Sediment RBC/Erythrocytes Urine Sediment WBC/Leucocytes
Urine	Albumin (quantitative)

Table 2. Laboratory Tests (Continued)

Category	Test Name
Infection screening	Hepatitis B Surface Antigen (qualitative) ^a Hepatitis B Surface Antibody (qualitative) ^a Hepatitis B Core Antibodies total (qualitative) ^a Hepatitis B Virus DNA (quantitative) ^{a,b} Hepatitis C Antibodies (qualitative) ^a Hepatitis C Virus RNA (quantitative) ^a HIV-1, and HIV-2 Antibody (qualitative) ^a PPD or QuantiFERON [®] -TB ^c

- a. Hepatitis B, Hepatitis C and HIV testing will be performed at screening.
- b. If Hepatitis B Surface Antigen is negative but Hepatitis B Core Antibodies total is positive and/or Hepatitis B Surface Antibody is positive, Hepatitis B Virus DNA will be quantified. If Hepatitis B Virus DNA level is undetectable at screening, the subject can participate in this trial. In these cases, HBV DNA level will be monitored at least every 6 months. If positive, the subject's treatment will be discontinued. If Hepatitis C Virus Antibodies is positive, Hepatitis C Virus RNA will be quantified. If Hepatitis C RNA level is undetectable at screening, the subject can participate in this trial. In these cases, HCV RNA level will be monitored at least every 6 months. If positive, the subject's treatment will be discontinued.
- c. TB testing will be performed at screening, Visit 12, 16, 20 and Week 184.
- d. Urine pregnancy test will be performed at all dosing visits.

Other Safety Parameters

Local Tolerability

Local tolerability at the administration site of the subcutaneous injection will be assessed by the investigator according to "swelling," "induration," "heat," "redness," "pain," or "other findings" at the specified visits as noted in [Appendix C](#). This assessment should be done pre-dose.

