Although rare, a potential for drug-induced liver injury (DILI) is under constant surveillance by sponsors and regulators. Therefore, this trial requires timely detection, evaluation, and follow-up of laboratory alterations in selected liver laboratory parameters to ensure subjects' safety.

In conclusion, the benefit-risk profile is considered appropriate for this stage of clinical development.

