5.0 Investigational Plan

5.1 Overall Study Design and Plan: Description

This trial is a randomized, open-label study of two different dose regimens of risankizumab, 150 mg (2 syringes, 75 mg each) or 75 mg (1 syringe) at Week 0, 4 and every 12 weeks in two populations (subjects with GPP and with EP). Starting after the Week 16 visit, subjects on 75 mg may increase dosage to 150 mg. In total, at least 16 subjects, 8 with generalized pustular psoriasis and 8 with erythrodermic psoriasis will be randomized in this trial.

Subjects are included in the trial once they have signed the informed consent. Subjects suitable after screening will be eligible to participate.

Figure 1. Trial Design

Visit Schedule

All subjects are to adhere to the visit schedule as specified in the [Appendix C](#). Each visit date (with its window) is to be counted from Day 1. If any visit has to be rescheduled, subsequent visits should follow the original visit date schedule. Additional visits for the purpose of re-testing of laboratory parameters or AE monitoring may be included as deemed necessary by the investigator.

Details of Trial Procedures at Selected Visits

Study procedures to be performed at each visit are listed in [Appendix C](#) and the respective protocol sections. Refer to Section [5.3.1.1](#) for explanations of procedures. Additional details on procedures at selected visits are provided below.

Measurement of vital signs should precede blood sampling and be assessed pre-dose at all dosing visits.

Patient reported outcomes (PRO)s should be completed by the subject on his/her own in a quiet area/room before any other visit assessments or treatments, and, if possible, before any interaction with the investigator or other members of the study team. At Visit 2 these questionnaires should be obtained before having the subject randomized.

Screening and Run-In Period(s)

No trial procedures should be done until the subject has consented to taking part in the trial.

Once consented, the subject is considered to be enrolled in the trial and has started screening. The subject number should be recorded on the enrollment log and registered in the Interactive Response System (IRT) as a screened subject.

The Screening Period (Visit 1) is from Day –42 to Day –1. Visit 1 procedures may be extended to two physical visits, if needed. Re-screening will be permitted.

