Visits 2, 4, 6, 8, 10, 12, 16, 20, end of treatment (EOT), Week 184 follow-up visit and Week 188 follow-up visit will be performed in fasted state (8 hours no food and only water). If a subject comes in non-fasted where a fasting condition is required, the visit should be performed, the non-fasted condition documented on the laboratory requisition, and the subject reminded about the expected conditions. At Visits 3, 5, 7, 9, 11, 13, 14, 15, 17, 18, 19, 21, only white blood cell count (WBC), serum C-reactive protein (CRP) and serum albumin ("targeted" lab) will be collected and fasting is not required for these labs.

Urine pregnancy testing for all woman of child-bearing potential will be conducted on-site prior to every dosing and must be negative to further treat the subject. A positive urine test must be confirmed with a serum pregnancy test.

Randomization via IRT and administration of study medication should be the last activity at Visit 2.

Venipuncture (i.e., safety laboratories, PK, anti-drug antibody [ADA]), should be the last procedure prior to study drug administration.

Follow Up Period and Trial Completion

For all randomized subjects termination of trial medication and trial completion must be recorded on the corresponding eCRFs.

Early Treatment and Trial Termination

Subjects who prematurely discontinue (PD) treatment prior to the planned [Appendix C](#) visit schedule will complete EOT visit procedures instead of the planned treatment period

visit. If study medication is discontinued, every effort should be made to have the subject continue in the trial and complete all of the follow remaining trial and follow up visits. If a subject cannot or will not continue in the trial, these subjects should be registered as withdrawn/discontinued in IRT. These subjects should be registered as withdrawn in IRT and return to the clinic for Week 188 Follow-Up visit 16 weeks after last dose of study medication.

Trial Completion

Subjects who finish the randomized treatment period will return to the clinic for Week 184 Follow-Up Visit and Week 188 Follow-Up Visit. Completion is defined as a subject having completed the Week 188 Follow-Up visit.

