6.1.1.3 Adverse Events of Special Interest

The term adverse events of special interest (AESI) relates to any specific AE that has been identified at the compound level as being of particular concern for prospective safety monitoring and safety assessment within this trial, e.g., the potential for AEs based on knowledge from other compounds in the same class. Ongoing evaluation of adverse events may identify future AESI.

The following are considered as AESI:

Hepatic Injury

A hepatic injury is defined by the following alterations of hepatic laboratory parameters:

- an elevation of aspartate aminotransferase (AST) and/or alanine aminotransferase (ALT) > 3 -fold upper limit of normal (ULN) combined with an elevation of total bilirubin > 2 -fold ULN measured in the same blood draw sample, and/or
- marked peak aminotransferase (ALT, and/or AST) elevations ≥ 10 -fold ULN.

These lab findings constitute a hepatic injury alert and the subjects showing these lab abnormalities need to be followed up according to instructions from the sponsor including completion of the hepatic adverse events form.

In case of clinical symptoms of hepatic injury (icterus, unexplained encephalopathy, unexplained coagulopathy, right upper quadrant abdominal pain, etc.) without lab results (ALT, AST, total bilirubin) available, the investigator should make sure these parameters are analysed, if necessary with an unscheduled blood test. Should the results meet the criteria of hepatic injury alert, investigators are advised to provide a hepatic workup as directed by the Sponsor.

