	V1	V2	V3	V4	V5	V6	V7	V8	V9	V10	V11	V12	V13	V14	V15	V16	V17	V18	V19	V20	V21			
Visit	0	4	8	12	16	22	28	34	40	46	52	64	76	88	100	112	124	136	148	160	172	184	188	
Week	0	4	8	12	16	22	28	34	40	46	52	64	76	88	100	112	124	136	148	160	172	184	188	
Day	-42 to -1	1	28	56	84	112	154	196	238	280	322	364	448	532	616	700	784	868	952	1036	1120	1162	1246	1274
Visit window (days)	± 3	± 7	± 7	± 7	± 7	± 7	± 7	± 7	± 7	± 7	± 7	± 7	± 7	± 7	± 7	± 7	± 7	± 7	± 7	± 7	± 7	± 7	± 7	± 7
Last injection of trial medication ¹¹																								
Trial completion																								
Vital status ¹²																								

1. At Visit 1, all subjects at all sites will be evaluated via CASPAR for history of psoriatic arthritis as detailed in [Appendix F](#).
2. Refer to Section [5.3.1.1](#) for weight procedures.
3. Physical examination: C = complete, T = targeted. Refer to Section [5.3.1](#).
4. Vital signs should precede blood sampling and be assessed pre-dose at all dosing visits. At Visit 2 and Visit 3, additional vital sign assessments should be taken at 5 minutes post-dose and 60 minutes post-dose. Subjects should be closely monitored for signs and symptoms of hypersensitivity reactions for approximately 2 hours after the first dose administered and 1 hour following all other doses of study drug.
5. Infection screening consists of Hepatitis B Surface Antigen (qualitative), Total Hepatitis B Core Antibodies (qualitative), Hepatitis B Surface Antibody (qualitative), Total Hepatitis C Virus RNA (Quantitative) reflex, Hepatitis C Virus RNA (Qualitative), Hepatitis C Antibodies (Qualitative), Hepatitis C Antibody (Qualitative), PPD or Quantiferon-TB. Hepatitis B, Hepatitis C and HIV testing will be performed at screening, Visit 12, 16, 20 and Week 184.
6. Serum pregnancy testing in all female subjects at screening and if urine pregnancy test is positive. Urine pregnancy testing will be done in women of child-bearing potential prior to administration of study drug at all dosing visits and at each Follow-Up Visit.
7. C = complete, T = targeted. Targeted lab samples should be limited to WBC, serum CRP and serum albumin for the measurement of JDA. Subjects should be fasting for at least 8 hours prior to the blood sample being taken at the "complete" visits, except for screening. If not fasted mark on laboratory requisition form.
8. On dosing visits, PK and ADA sampling should be taken approximately within 1 hour prior to administration of study drug.
9. Collected for Substudy GPP.

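### Between Weeks 52 and 148 the scheduled liver tests are 48 weeks apart although blood is drawn every 12 weeks; adding them to existing draws is a cheap improvement

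*Protocol*

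**What the plan says.** Protocol 5.3.1.1 (Safety Laboratory Parameters) lists the complete panel at Visits 1, 2, 4, 6, 8, 10, 12, 16, 20, EOT and the Week 188 follow-up. Protocol Table 2 puts AST, ALT, alkaline phosphatase and total bilirubin in that panel. For the other treatment visits: "At Visits 3, 5, 7, 9, 11, 13, 14, 15, 17, 18, 19, 21, only WBC, serum CRP and serum albumin will be collected". Appendix C, note 7, gives the purpose of the smaller draw: "Targeted lab samples should be limited to WBC, serum CRP and serum albumin for the measurement of JDA". Section 5.1 adds that "fasting is not required for these labs".

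On the aim of liver monitoring, Protocol 3.2 says that "this trial requires timely detection, evaluation, and follow-up of laboratory alterations in selected liver laboratory parameters". No interval is attached. Hepatic injury is the only AESI listed in 6.1.1.3, and it is defined by AST, ALT and total bilirubin alone.

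The protocol has other routes to a liver test or related check:

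- Liver symptoms without results at hand (6.1.1.3): "the investigator should make sure these parameters are analysed, if necessary with an unscheduled blood test".
- Investigator discretion (5.1): "Additional visits for the purpose of re-testing of laboratory parameters or AE monitoring may be included as deemed necessary by the investigator".
- A known abnormal result (5.3.1.1): "Clinically relevant abnormal laboratory test results must be confirmed using an unscheduled visit laboratory kit", with repeats afterwards.
- Eligible subjects with positive hepatitis B serology (Table 2, note b): "HBV DNA level will be monitored at least every 6 months". HCV RNA is followed in the same way. Neither rule adds enzymes.

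SAP Table 2 gives analysis windows for laboratory tests other than WBC, CRP and albumin. From Week 52 to Week 148 its only target days are 365, 701 and 1037.

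**The concern.** Liver testing is close together in the first year and then becomes four times as sparse, while dosing stays 12-weekly and a needle still goes in at every dosing visit. The protocol gives no reason for the change. Section 5.5.4 allows non-responders on 75 mg to move to 150 mg at visits after Week 16 and states no end to that option. A dose doubled at Week 64 would have its next scheduled liver test at Week 100, 36 weeks later.

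None of the routes listed above schedules a test for a new elevation without symptoms in a subject with no earlier abnormal value. Because the hepatic injury AESI is a laboratory definition, it cannot be recognised without the blood test. What is at stake is the safety of an individual subject, who may be dosed on through an unrecognised elevation, and the completeness of the liver shift tables, the liver listing and the Hy's Law listing in SAP 11.3.2. The primary endpoints are not affected.

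**Working it through.** **1. Spacing of the liver tests.** The Appendix C week row gives Visit 2 = Week 0, 4 = 8, 6 = 16, 8 = 28, 10 = 40, 12 = 52, 16 = 100, 20 = 148, and EOT = 172 by label.

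- Complete-panel weeks after screening: 0, 8, 16, 28, 40, 52, 100, 148, 172, 188.
- Gaps: 8, 8, 12, 12, 12, **48, 48**, 24, 16 weeks.
- Check against SAP Table 2: (701 − 365)/7 = 48 and (1037 − 701)/7 = 48. The two documents agree.
- With visit windows of ±7 days, a 48-week gap can run from 46 to 50 weeks.

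The safety-laboratory row of Appendix C is broken in the text available, so this rests on the 5.3.1.1 text, the week row and SAP Table 2.

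**2. Doses and draws inside each gap.** Dosing at Weeks 0 and 4 and every 12 weeks after gives 16, 28, 40, 52, 64, and so on. Between Weeks 52 and 100 there are doses and targeted draws at 64, 76 and 88; between 100 and 148, at 112, 124 and 136. Section 5.1 puts venipuncture last before the injection, and 5.3.1.1 uses a central laboratory. The dose on the test day may therefore be given before the result is known.

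**3. Delay and detection.** Assumptions: a silent episode starts uniformly over Weeks 52 to 148, lasts d weeks, and no unscheduled test is done. For a test interval of g weeks, mean delay to the next scheduled test is g/2, the maximum is g, and the chance that a scheduled test falls within the episode is min(1, d/g).

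| | g = 48 (plan) | g = 24 (add Visits 14, 18) | g = 12 (add six visits) |
|---|---|---|---|
| Mean / maximum delay, weeks | 24 / 48 | 12 / 24 | 6 / 12 |
| Further doses before the draw, mean / maximum | 1.5 / 3 | 0.5 / 1 | 0 / 0 |
| Same, counting the test-day dose | 2.5 / 4 | 1.5 / 2 | 1 / 1 |
| Detected, d = 4 | 8% | 17% | 33% |
| d = 8 | 17% | 33% | 67% |
| d = 12 | 25% | 50% | 100% |
| d = 24 | 50% | 100% | 100% |
| d = 36 | 75% | 100% | 100% |
| d = 48 | 100% | 100% | 100% |

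The mean dose counts average over the dosing intervals in a gap: (3 + 2 + 1 + 0)/4 = 1.5 and (1 + 0)/2 = 0.5.

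**4. Where added results would fall in SAP Table 2.**

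- Weeks 64 and 76 (Days 449, 533): Week 52 window, [324, 533].
- Weeks 88, 112 and 124 (Days 617, 785, 869): Week 100 window, [534, 869].
- Week 136 (Day 953): Week 148 window, [870, 1100].

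SAP 6.0 keeps only the value closest to the nominal day in each window. The added results would therefore drop out of the by-visit summaries whenever the Week 52, 100 or 148 panel is present.

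**The case against.** The sponsor's case is respectable. Testing is concentrated in the first 52 weeks, which Protocol 3.0 names as the period for the trial's data, and relaxing it later is a recognisable choice. The liver concern is generic: Protocol 3.2 calls drug-induced liver injury rare, the common adverse events it reports from Phase 1 and 2 include nothing hepatic, and SAP 11.2.1 explains the interest in liver injury as one that applies to products in general. The choice of 12 weeks is also open to challenge, since a 24-week gap by label is left between Weeks 148 and 172. All of this stands. It makes the point a suggestion, and it makes a 24-week schedule a fair lighter option.

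A reader might infer more than the documents support:

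- **That the protocol breaks its own rule.** Timeliness is not given a number, so there is nothing to break, and Protocol and SAP are consistent.
- **That liver safety is unmonitored after Week 52.** Symptoms, known abnormal results and investigator judgement all lead to tests. Only the silent new elevation is left out.
- **That a number of missed cases can be stated.** The documents give neither a rate nor a duration of liver elevations.
- **That 12-weekly testing would stop dosing at once.** The test-day dose may still precede the result. The saving is 1.5 doses on average, whether or not that dose is counted.
- **That the SAP liver outputs would discard extreme values.** SAP 11.3 asks for the most extreme on-treatment value, and 11.3.2 uses maximum values and lists every subject who meets a criterion. The window problem concerns the by-visit summaries.

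**Conclusion.** The point holds as a cheap improvement, not as an error. The 48-week spacing is a fact of both documents. It is four times the longest gap used up to Week 52, and no safeguard schedules a test for a silent new elevation. At worst, three further doses precede the next scheduled draw and a fourth precedes its result; with 12-weekly tests these become none and one. Short episodes would mostly be missed by scheduled testing, and long ones found late. The delay and detection figures depend on uniform onset and no unscheduled testing. They describe the schedule and do not predict events. With about 16 subjects few events would be expected, but the consequence for one subject could be serious and the remedy is small.

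**What to change.** **Protocol.** In 5.1 (Treatment Period), 5.3.1.1, and the Appendix C grid and note 7, add ALT, AST, alkaline phosphatase and total bilirubin to the targeted draw at Visits 13, 14, 15, 17, 18 and 19 (Weeks 64, 76, 88, 112, 124, 136), without fasting. The wording must name the visits, because Visits 3, 5, 7, 9 and 11 are targeted too. A lighter option is to add Visits 14 and 18 only (Weeks 76 and 124), for a maximum gap of 24 weeks.

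**SAP.** For by-visit summaries of these four analytes, replace the Table 2 windows from Week 52 with:

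- Week 52: [324, 407].
- Weeks 64 to 136: the Table 1 windows.
- Week 148: [996, 1100].
- Week 172: [1101, 1205].

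These leave no day uncovered. If only Visits 14 and 18 are added, reset the windows at the midpoints between target days: (365 + 533)/2 = 449, (533 + 701)/2 = 617, (701 + 869)/2 = 785 and (869 + 1037)/2 = 953. That gives Week 52 [324, 449], Week 76 [450, 617], Week 100 [618, 785], Week 124 [786, 953] and Week 148 [954, 1100].

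**Cost.** A protocol amendment with IEC/IRB approval before use (Protocol 9.1), a laboratory requisition change, a SAP window edit, and some minor alerts to follow up. No visit or venipuncture is added. That the present sample volume suffices is an assumption, because the Laboratory Manual is not among the documents; if it does not, a larger tube at the same draw would be needed.
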